The Effects of Phosphatidylserine Expression on Older Red Cell Units in Adults with Sickle Cell Disease

Protocol Version 11 – Oct 10, 2023

Study Sponsor: NHLBI

Principle Investigator: [name], MS
Clinical co-investigators: [name], [name]

Conducted at the University of North Carolina Sickle Cell Clinic,
And Emory University

A randomized trial to determine if there is a mechanistic
or clinically important difference between the PS-high vs. PS-low units
on patient immune systems & clinical outcomes

Table of Contents

X. Synopsis and Study Schema -	1
1. BACKGROUND AND SIGNIFICANCE -	6
2. OBJECTIVES -	9
3. STUDY POPULATION -	11
4. TRIAL ENROLLMENT -	11
5. INTERVENTIONS -	13
6. SCHEDULE OF MEASUREMENTS -	14
7. SPECIMEN COLLECTION PROCEDURES -	18
8. ADVERSE EVENT CRITERIA AND REPORTING -	18
9. SAFETY MONITORING AND STOPPING GUIDELINES -	22
10. STATISTICAL CONSIDERATIONS -	22
11. DATA COLLECTION AND VALIDATION -	25
12. PROTECTION OF HUMAN SUBJECTS -	25
13. INVESTIGATOR RESPONSIBILITY -	25
14. MONITORING AND QUALITY CONTROL -	26
15. RECORDS AND REPORTS -	26
16. REFERENCES -	28

Quick List of Abbreviations:

RBC – Red blood cell
SCD – Sickle cell disease
PS – Phosphatidylserine
PE – Phosphatidylethanolamine
NTBI – non transferrin bound iron
MFI – mean fluorescence intensity

Concept Synopsis and Study Schema

The desired impact of red blood cell (RBC) transfusion in patients with sickle cell disease (SCD) is to reduce the burden of patient sickled red cells with the goal of reducing stroke risk and reducing the burden of frequent vaso-occlusive pain events that is otherwise refractory to other treatment modalities. However, controversy exists over transfusions with blood banked for short vs. long storage intervals. Pre-clinical animal studies and observational human models suggest that increased phosphatidylserine exposure (PS), seen often from red cells units with longer storage intervals, may lead to downstream immune effects that have detrimental consequences, such as increased clinical infections. No randomized prospective human study has attempted to correlate age of transfused RBCs with PS-exposure, and then evaluate how this exposure modulates patient immune systems and subsequent clinical outcomes.

Primary Hypothesis:

There is a clinically significant difference between the effect of PS-high RBCs vs. PS-low RBCs on patient macrophages.

Study Schema:

Trial design: Adults and adolescents (post puberty) with SCD who are treated with outpatient red cell transfusions will be randomized in blocks of 5 (S. Piantadosi block randomization software, 2010) to receive ≥ 30 day or ≤ 10 day old units for 3 months (3 consecutive transfusion events). **The study statistician** will provide the blood bank with the schema who will then be responsible for providing the units for these subjects. Participants and all other investigators will be blinded to treatment assignment.

Two baseline venous blood samples will be obtained to be used as a baseline measurement of the patients underlying inflammatory status. The first will be drawn about 1- week prior to the first randomized transfusion, and the second sample just prior to the first randomized transfusion. Subjects will be asked to hold their iron chelation 72 hours before the study transfusion. Pre-transfusion, sterile samples will be extracted from red cell units. Patient venous blood samples will be also obtained 2 hours post transfusion, 24 hours post-transfusion, and 2 weeks post-transfusion (**Table 1**). Participants will complete standardized diaries daily to document symptoms of infection, SCD pain, medications and emergency department (ED) or hospital use. Diaries will be collected and participants will be assessed with each transfusion encounter, up to 3 transfusion events, and 4 weeks after the last transfusion. To ensure compliance, coordinators will

contact subjects regularly to remind them to complete diaries. All data will be captured with standardized case report forms and entered into an electronic database.

Subject Recruitment and Anticipated Numbers: We intend to recruit and enroll 40 subjects. Participants will be recruited from the Adult SCD Clinic at UNC and Emory/Grady Health System. We expect that UNC will recruit between 5-10 subjects over the next 2 years (15 subjects have already been enrolled at Medical College of Wisconsin), and Emory will recruit between 10-20 subjects to reach the study goal of 40 randomized subjects.

Subject Inclusion/exclusion criteria:

Inclusion criteria:

- 1) Ages 16 to 60 years old
- 2) Subject must have sickle cell anemia confirmed by hemoglobin analysis
- 3) Must be receiving red cell transfusion therapy
- 4) Must be outpatient at the time of study transfusions

Exclusion criteria:

- 1) History of severe reactions to transfusion therapy
- 2) Receive red cell transfusions that are crossmatch incompatible
- 3) Current participation in another therapeutic trial for sickle cell disease
- 4) Current pregnancy
- 5) History of HIV infection
- 6) Having an uncontrolled inter-current illness, or psychiatric illness/social situations that would limit compliance with study requirements as determined by the principal investigator.

Study procedures:

Red cell unit preparation: Red cell units for transfusion will be crossmatch-compatible, sickle-negative, and phenotype-matched for D, C, E, and K red cell antigens per current hospital protocols. Red cell unit age will be documented by the blood bank at the time of randomization. Study transfusions will take place *only* in the outpatient infusion clinic.

Pain and infection diary: The diary is adapted from a model widely used in SCD studies. Daily, participants will rate pain on a numeric ordinal pain rating scale (0-10), indicate whether the pain was consistent with a “crisis,” indicate whether they utilized a healthcare facility, and record the amount of opioids used. Infection symptoms will also be documented daily along with the type, duration, and dose of antibiotics, if applicable.

Physical exam: A basic, focused, physical exam will be performed on each subject by the PI or trained delegate prior or during each transfusion and prior to the completion of the study. The physical exam will assess a general review of systems, a review of the pre-transfusion vital signs, and a basic evaluation of patient general status, heart, lung,

and neurological organ systems. We will also document if the patient has an indwelling catheter.

Blood measurements:

Unit samples: Red cell characteristics: 2 ml blood from each red cell unit will be obtained from 6 sterile unit links pre-transfusion. RBC PE and PS surface exposure, and plasma microparticles will be quantified by flow cytometry using the LSR2-green, and all flow analyses will be recorded using FACSDiVa software. The plasma fraction from each unit sample will be diverted to EPR (Bruker Elexys X-band system, Billerica, MA, USA), a Bio-Plex cytokine assay kit (Bio-Rad Laboratories), and a fluorescent immunoassay (DxFerr kit) to measure concentrations of free heme/hemoglobin, cytokines (IL-1, IL-6, IL-8, MCP-1), and NTBI, respectively. A small sample will also be frozen for future metabolomic analysis.

Patient Samples: 10-30 ml per lab draw of whole blood will be obtained for each blood draw as defined in **Table 1**, and will be stored per tube storage requirements. . Blood will be obtained by port or peripheral access as available. Patient white cells will be isolated with established Ficoll separation techniques.. White cells will be tested by flow cytometry as above for key markers of activation (macrophages: CD64, CD62L, CD80, CD86, Tim1, neutrophils: The plasma fraction from each sample will be diverted to EPR (Bruker Elexys X-band system, Billerica, MA, USA), a Bio-Plex cytokine assay kit (Bio-Rad Laboratories), and a fluorescent immunoassay (DxFerr kit) to measure concentrations of free heme/hemoglobin, cytokines (IL-1, IL-6, IL-8, MCP-1), and NTBI, respectively. Clinical measurements obtained from patients will also include: CBC (4ml EDTA), reticulocyte count (4ml EDTA), HbS% (3ml EDTA), haptoglobin (1ml red top), chemistry labs (ferritin (0.5ml red top), iron saturation (1ml red top), lactate dehydrogenase (1ml red top), high sensitivity CRP (HS-CRP, 1ml red top)), urinalysis (12 ml) and blood culture (8-10ml/bottle). These clinical labs will be measured at intervals specifically defined in **Table 1**. Individual human samples of plasma and RBC will also be frozen and sent to [name] at the University of Colorado Denver to measure lipid metabolites and metabolomic profiles pre vs. post transfusion as an additional exploratory goal of this trial. The laboratory of [name] and his representatives will be receiving 30-200 individual samples of plasma and RBCs for this purpose. All samples will be de-identified.

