2. OBJECTIVES

2.1: Primary Aims

Note: This randomized clinical study should be considered a feasibility study to determine the ability to design and run a protocol of this nature. Each Aim was specifically selected

to maximize the possibility that novel information could be obtained from this trial. However, power calculations and associated precision estimates should be considered preliminary, as the data derived from this study will inform the calculations necessary to design a larger, more definitive study.

Aim 1:

To characterize the physiologic differences between ≥ 30 vs ≤ 10 day-old units. As part of the randomized study, we will measure PS exposure on donor red cells, as well as PE, microparticles, plasma free hemoglobin, heme, and NTBI. We hypothesize that ≥ 30 day-old units will have significantly more **biochemically old units** (see section 10 for the definition) than <10 day-old units. With a total sample size of 40 patients (20 in each group), we will have at least 80% power ($\alpha=0.05$) to detect a difference of at least 47% between the two randomized groups for biochemically old red cell units (close to a 100% difference is expected).

Aim 2:

To quantify whether physiologic differences between ≥ 30 day-old units versus ≤ 10 day-old units promote immune cell activation in transfused adults with SCD. We will perform flow cytometry to measure the activation of monocytes and neutrophils, as well as measure cell-free hemoglobin, heme and NTBI on blood samples before, 2, and 24 hours after transfusion. We hypothesize that those administered ≥ 30 day-old (biochemically old) units will have a greater increase in the number of CD62L + activated monocytes at 2 hours post-transfusion compared to those administered <10 day-old units. With a sample size of 40 patients, we will have 80% power ($\alpha=0.05$) to detect a change in MFI ratio of 1.35.

Aim 3:

To explore whether the physiology of ≥ 30 day-old units versus ≤ 10 day-old units is associated with adverse clinical outcomes in transfused adults with SCD. We will perform a systematic evaluation of hospital admissions, pain scores, medications, and clinical symptoms prior to each transfusion and at the end of the study period (**Table 1**). We hypothesize that reports of infection will be greater in subjects randomized to receive ≥ 30 day-old older units.

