10.2.1 Primary Outcome Analysis

Key variables of interest:

PS – Measured as a percent of RBC positive

PE – Measured as a percent of RBC positive

Microparticles – Measured by number positive per microliter
CD62L – Measured as percent of monocytes positive
Plasma free hemoglobin – Measured as mg/dL
Non-transferrin bound iron – Measured as mg/dL
Rate of clinical infections – Measured as number per days on study

Aim 1:

The primary outcome measure is the proportion of biochemically old red cell units. Previous studies and our own work have suggested that PS, PE, and microparticles increase in a sigmoidal fashion over time.^{7,10} For this study, the cut-off for a biologically old unit would be the point at which the sigmoidal curve enters its log phase, which for PE, PS, and microparticles will be the mean value at day 21, or 8%, 3%, and 3/ μ L respectively based on these preliminary studies. This cutoff is biologically meaningful and is supported temporally by the metabolic changes that occur with red cell storage.¹¹⁹ Consequently, biochemically old units will be defined as having either a surface PE, surface PS, or a microparticle concentrations \geq the *a priori*-defined cutoff. We will compare the transfusions provided to the two groups (the proportion of biochemically old units when stored \geq 30 days compared to when stored \leq 10 days) using a Fisher exact test at an alpha of 0.05. Power: With a total sample size of 40 patients (20 in each group), we will have at least 80% power ($\alpha=0.05$) to detect a difference of at least 47% between the two randomized groups for biochemically old red cell units (close to a 100% difference is expected).

Exploratory: We will calculate the mean, minimum, and maximum levels of PS, PE, and microparticles for each study group, and we will compare the secondary outcome measures of plasma free hemoglobin, heme, and NTBI and also PS, PE, and microparticle concentrations using a two sided two sample t-test at an alpha of 0.05. We will also plan for auxiliary analyses that characterize the relationship between the PS level and the age (days) of the RBC units. This analysis will focus on estimation of the mean PS, PE, and microparticle level as a function of age (days), visualization of the data values, estimation of correlation coefficients, and evaluation of how well age (days) predicts PS, PE, and microparticle levels.

Aim 2:

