The primary outcome measure is the change in CD62L (activated) circulating monocyte/macrophage MFI at 2 hours post-transfusion compared to the subject pre-transfusion. We will compare the two groups (\geq 30 day-old compared to \leq 10 day-old unit exposure) using a two sample two-sided t-test of the log at an alpha of 0.05. Power: We will have at least 80% power to detect a change in the ratio of 1.35 post-transfusion if the variability is similar to that seen in our preliminary data.

Exploratory: We will use a general(ized) linear model to include biochemically old units transfused (Aim 1 outcome), regardless of unit age, as a covariate in our analysis. Other co-variates in this model will include free heme, cell free hemoglobin, and NTBI. We will similarly compare other obtained activation measures as outcomes: activation markers for monocytes, neutrophils (as listed in section 6) and measured plasma cytokine

concentrations (section 6). We will also plan for auxiliary analyses of the outcome variables in which the explanatory variable is the age (days) of the RBC units --to characterize the degree to which age (days) can accurately predict the clinical and physiologic outcome measures defined. Lastly, as an exploratory aim, we will evaluate the *in vivo* change in recipient red cell PE/PS positivity at 2 and 24 hours post transfusion.

Aim 3:

The primary outcome variable is the rate of post-transfusion infections in the patient. The primary estimand is the treatment effect defined as the difference between the regimen-specific proportions of patients in the target populations that would experience post-transfusion infections. This population parameter will be estimated as a function of the proportions observed in the sample of patients studied. The point estimate will be reported along with the corresponding 95% confidence interval estimate. The presence of an indwelling catheter will be used as a key co-variate in this analysis. *Power:* A difference of 20% will be of clinical interest. We do not expect to have adequate power for this pilot study but at an alpha of 0.05 with 20 subjects in each group we will be able to detect a difference of 47% between the proportions.

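### Blocks of 5 for two arms do not guarantee the 20 per group assumed for Aims 1 and 3; the effect on power is minor and the correction is nearly free

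*Combined protocol and SAP*

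**What the plan says.** The trial design paragraph of the Concept Synopsis describes two arms (units stored at least 30 days, or at most 10 days) and says subjects will be "randomized in blocks of 5". It gives neither an allocation ratio nor the make-up of a block. Section 4.2, which covers stratification and randomization, gives no block size or ratio. It rules out stratification by gender, age, ethnicity and hemoglobinopathy type, and does not mention site.

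The group sizes come from the power statements:

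- **Aim 1:** Section 2.1 has "20 in each group". Section 10.2.1 begins "With a total sample size of 40 patients (20 in each group" and claims at least 80% power "to detect a difference of at least 47% between the two randomized groups for biochemically old red cell units", tested "using a Fisher exact test at an alpha of 0.05".
- **Aim 3:** Section 10.2.1 gives a detectable difference of 47 points "with 20 subjects in each group".
- **Aim 2:** Section 2.1 gives only a total: "With a sample size of 40 patients, we will have 80% power", for an MFI ratio of 1.35. Section 10.2.1 repeats the ratio without a number of patients.
- **Section 9** uses a different size, 30 subjects with 15 per arm.

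The Synopsis also reports that 15 subjects have already been enrolled at a first site, out of a target of 40.

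**The concern.** Blocking is used so that the arms stay close to equal as the trial fills. With two arms, that needs an even block. In a block of five the nearest possible split is 3:2, so each completed block leaves the arms one patient apart, and the final balance depends on which arm each block favours. The protocol has no rule for that. The stated randomization scheme therefore does not lead to the stated 20 per group.

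Unequal arms reduce the precision of a two-group comparison for a given total. A reader also cannot tell whether equal allocation was intended and the block size is a slip, or whether something else was meant. If lists are kept separately by site, which the protocol does not say, a first site that filled three complete blocks of five could be no closer than 8:7, and incomplete blocks at the other sites could add to the difference.

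**Working it through.** **Inputs from the documents:** block size 5; 40 patients; 20 per group and 47 points (Aims 1 and 3); Fisher exact test at alpha 0.05 (Aim 1), taken as two-sided; two-sided two-sample t-test on the log scale at alpha 0.05, with ratio 1.35 and 80% power (Aim 2).

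**Assumptions:** blocks are as near equal as possible (3:2 or 2:3); each block's direction is an independent fair coin; there is one list for the trial; base rates and the log-scale SD, which are not given, are set as described below.

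**1. The plan's own figure.** No base rate is given for the 47-point difference, so the rates are centred on one half (26.5% vs 73.5%). The continuity-corrected normal formula then needs 21 per group, against 20 stated. Exact Fisher power at 20:20 is 77.3% for these rates, which are the least favourable, 87.0% for 10% vs 57%, and 91.7% for 5% vs 52%. The stated figure is reproduced to within rounding and choice of base rate.

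**2. Possible splits.** 40 / 5 = 8 blocks. If k blocks give three patients to arm A, then arm A has 3k + 2(8 − k) = 16 + k patients. With k ~ Binomial(8, 0.5), P(k) = C(8, k) / 256.

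| Split (either direction) | Probability |
|---|---|
| 20:20 | 70/256 = 27.3% |
| 21:19 | 112/256 = 43.8% |
| 22:18 | 56/256 = 21.9% |
| 23:17 | 16/256 = 6.3% |
| 24:16 | 2/256 = 0.8% |

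A split of 22:18 or worse has probability (56 + 16 + 2)/256 = 74/256 = 28.9%. A split of 22:18 or closer has probability (70 + 112 + 56)/256 = 238/256 = 93.0%.

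**3. Aim 2 power.** The SD is back-solved from the plan's own claim. Power is P(T > t(0.975, 38)), where T is noncentral t on 38 degrees of freedom with noncentrality ln(1.35) / [SD × √(1/n₁ + 1/n₂)]. Setting this to 80% at 20:20 gives a log-scale SD of 0.330. The noncentrality is 2.875 at 20:20 and 2.817 at 24:16.

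| Split | Aim 2 power | Ratio detectable at 80% power |
|---|---|---|
| 20:20 | 80.0% | 1.350 |
| 21:19 | 79.9% | 1.351 |
| 22:18 | 79.6% | 1.352 |
| 23:17 | 79.1% | 1.355 |
| 24:16 | 78.4% | 1.358 |

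Weighted by the probabilities in step 2, expected power is 79.8%. Relative efficiency at 24:16 is 4 × 24 × 16 / 40² = 0.96, so 40 / 0.96 = 41.7, or about 42 patients, would do the work of 40 in equal arms.

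**4. Aims 1 and 3.** The exact Fisher power for a 47-point difference at the least favourable rates is 77.3% at 20:20, 79.2% at 19:21, 79.9% at 18:22, 78.3% at 17:23 and 79.0% at 16:24. It does not fall with imbalance, because the exact test is discrete and the attained significance level shifts with the group sizes. The pooled normal approximation, which is free of that effect, falls from 87.4% at 20:20 to 86.2% at 16:24.

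**5. What even blocks would now achieve.** Suppose the 15 patients already enrolled were randomized in three blocks of five, and the remaining 25 are issued in blocks of 4 and 6 in random order. In simulation, 20:20 then occurs in about 37% of trials (against 27%), 22:18 or worse in about 13% (against 29%), and expected Aim 2 power is about 79.9%.

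**The case against.** A reader might infer that blocks of five make equal arms impossible. They do not: four blocks in each direction give exactly 20:20. A reader might also infer that every power statement fails with the block size. Only Aims 1 and 3 cite 20 per group, Aim 2 cites 40 in total, and Section 9 cites 15 per arm. And a reader might take 24:16 as the expected result. That needs all eight blocks to favour the same arm; a fixed 3:2 pattern would amount to deliberate unequal allocation, which the per-group figures contradict.

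The case for leaving the matter alone goes further. The power at stake is a fraction of a point in expectation. For Aim 1 the plan says "close to a 100% difference is expected", so no plausible split matters there. Aim 3 is declared underpowered from the start, and Section 2.1 calls the trial a feasibility study with preliminary power figures. Even blocks introduced now cannot force 20:20 either, because three odd blocks may already have been used and 25 is odd.

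All of that stands as an argument about size. It does not supply the missing ratio or block composition, and it does not reconcile an odd block with equal groups. The remark about separate site lists is conditional, because the documents do not say how lists are held.

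**Conclusion.** The point holds as a specification gap with a small statistical cost. The stated block size cannot give 1:1 within any block and does not guarantee the 20 per group assumed for Aims 1 and 3. Under random block direction, a split of 22:18 or worse has probability 29%. The average cost to Aim 2 is 80.0 − 79.8 = 0.2 points of power, and the largest is 80.0 − 78.4 = 1.6 points, with probability 0.8%.

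These figures rest on 3:2 blocks with random direction, one list, no drop-out (as the plan expects), and an SD inferred from the plan's own 80%. The documents do not support reading this as a loss of adequate power. It merits correction because the allocation rule and the group sizes do not fit together and the remedy costs almost nothing.

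**What to change.** 1. State 1:1 allocation in the Synopsis and in Section 4.2.
2. Generate all remaining allocations in even permuted blocks, for example sizes 4 and 6 in random order.
3. Say whether there is one list or one per site.
4. Report the actual split of the patients already randomized (to the statistician and the DSMB while the trial is blinded), and restate the power figures for the split now expected. Even blocks from here on reduce the imbalance but do not force 20:20.
5. If five per arm was meant, correct the text to blocks of 10; four such blocks give 20:20 exactly.

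The cost is one regenerated list and a few sentences in the protocol. No patients, visits or procedures are added. The difference between 20 per group in Section 10 and 15 per arm in Section 9 is a separate matter that can be reconciled in the same amendment.
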